8.9 Prostate MRI scans (Arm 2)

Patients within Arm 2 will be offered the option to undergo additional MR imaging of the pelvis in addition to any standard of care imaging acquired. In patients who agree to undergo additional scans, MRI scans will be performed on 2 occasions prior to the radical prostatectomy. MRI scans will be acquired on either the MR sim diagnostic scanner, on the MR Linac scanner or on both within The Christie NHS Foundation Trust.

The MR sequences obtained will include sequences for oxygen-enhanced MR, IVIM, DCE and BOLD and aim to detect hypoxic sub-regions of tumour that can be validated against pimonidazole staining regions following prostatectomy. Patients will be asked to will breathe 21% followed by 100% oxygen gas through an oxygen mask during the scan. They will receive a gadolinium-based contrast agent through an intravenous cannula. Scan time will not exceed 60 minutes per scan. Any patients not agreeing to undergo additional MRI scans are still able to be enrolled into Arm 2 of the trial.

8.10 Tissue Processing and Storage

The PrestoCHILL freezing device (Milestone Medical, Menarini Diagnostics, UK) will be used in order to access tumour content and select appropriate material for obtaining the highest quality DNA and RNA, retaining also an appropriate amount for FFPE evaluation and studies. Samples will be collected and stored at the Manchester Cancer Research Centre Biobank. Serum samples will be centrifuged and frozen at -20°C at the MCRC biobank. The other blood samples will be taken to the biobank at room temperature, *Streck* tubes and EDTA tubes will then be send to the CRUK Manchester Institute Cancer Biomarker Centre (CBC) ([name]).

The Christie **NHS**
NHS Foundation Trust

Prostate specimens will be routinely sectioned with a cryotome and sections for diagnostic routine H/E histopathology as well as additional sections for pimonidazole or alternative hypoxia staining method (such as GLUT1 immunohistochemical staining) and nucleic acid extraction for subsequent genomic/transcriptomic analysis cut. Bone specimens will be similarly frozen and analysed but cut on the cryotome using special *cryo tungsten carbide blades*. Tissue cryo-preservation, sectioning and processing will be carried out by the Histopathology Department at The Christie NHS Foundation Trust and Cancer Research UK Manchester Institute (CRUK MI).

8.11 Hypoxia Assessment and Analysis of Tumour Genome and Transcriptome

Fresh-frozen tumour samples will be analysed by both conventional histopathology and comprehensive assessment of the tumour genome and functional gene expression profile. 4-5µm sections will be taken for immunohistochemistry, 10 µm sections will be taken for nucleic acid extraction. A consultant histopathologist ([name], The Christie NHS Foundation Trust) will (i) confirm the diagnosis of prostate cancer and will allow for proper diagnostic work-up including grading according to the Gleason score (H/E staining) and (ii) allow assessment of the presence of intratumoural hypoxia as detected by immunohistochemical staining for pimonidazole. If the patient did not receive pimonidazole pre-biopsy then an alternative immunohistochemical stain such as GLUT1 will identify hypoxic areas. Hypoxic areas will be marked to guide microdissection for subsequent nucleic acid extraction from the respective slides.

Further analysis of the tumour DNA, RNA and functional transcriptome will include whole exome sequencing (WES), which may be carried out by a third party as appropriate, with all necessary agreements in place.

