7 RESEARCH AIMS

Assess the differential genomic aberrations and gene expressional alterations in hormone-naïve primary PCa and paired skeletal metastases.

Whole exome sequencing (WES) analysis will be performed and the results of the paired samples of the study patients will be compared in silico to ~500 patients with pT1-3 N0M0 disease from the CPC-GENE bioinformatics portal as a control set [11]. Moreover, to assess the gene expression profile of primary tumour and metastases, the whole RNA will be sequenced (RNAseq).

Determine whether co-existent intra-prostatic hypoxia, EMT and genomic instability is a co-factor in driving early spread

Hypoxic areas of primary tumour identified through either pimonidazole or other hypoxia labelling method such as GLUT1 immunohistochemical staining (if available, otherwise archival FFPE tissue from primary diagnostic biopsy) and metastatic tumour tissue will be micro-dissected and analysed by WES, RNAseq, and a targeted mRNA analysis to detect the Manchester 28-gene expression signature predicting for tumour hypoxia. Data pertaining to the co-occurrence in regions identified as hypoxic using immunohistochemical stains (such as pimonidazole or GLUT1), Copy Number Alterations, Single Nucleotide Variants and whole RNA expression profiles as well as the Manchester hypoxia 28-gene RNA signature will be compared.

Identification of co-existence of hypoxia in primary and metastatic tumour sites

Results of immunohistochemically identified hypoxic regions (through PIMO-staining or alternate staining method such as GLUT1) and the 28-gene RNA expression of the samples will be compared for each patient to identify co-existent hypoxia in primary PCa and paired bone metastases.

Assess the prevalence and origin of CTCs in early, aggressive (oligo-) metastatic disease

To increase sensitivity of detection marker-independent platforms will be used. CTCs will be isolated and molecularly profiled to determine whether they originate from primary tumour and/or from metastases. Moreover, CTC genomes will be mapped to primary/metastatic tumour regions identified as having high or low levels of hypoxia (through pimonidazole or other staining method) to determine if hypoxia (and hypoxia associated EMT) drives tumour cell dissemination.

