8 STUDY PROCEDURES & METHODOLOGY

8.1 Study Design

This is a prospective, non-randomised, single-centre, exploratory biomarker study. In Arm 1 this involves targeted tumour tissue sampling in men with either newly diagnosed, untreated metastatic prostate cancer involving patients with either high (cohort A; widespread metastatic disease) or low, oligometastatic (cohort B; ≤ 4 bone metastases) burden of disease. In Arm 2, targeted tumour tissue samples derived from prostate cancers biobanked as per standard MCRC biobanking protocol in 30 men undergoing a radical prostatectomy as part of their standard care.

In Arm 1, to minimize the interventional burden for the patients, patients will be amenable to have a combined diagnostic and research biopsy of the prostate in one session after routine imaging for diagnostic work-up comprising of a CT scan of abdomen and pelvis, bone scan and multi-parametric MRI of the prostate. Patients, who already had a diagnostic TRUS biopsy will be asked to provide research tissue samples during a second TRUS biopsy as part of the HYPROGEN study interventions. Patients declining a second prostate biopsy will be eligible and will undergo the bone biopsy only. Patient identification will be done through the respective multidisciplinary tumour (MDT) boards and patient referral pathways at Salford Royal, Oldham Royal and Wythenshawe Hospital as further outlined in section 9.1.

To yield highest possible biopsy accuracy and tissue amount and maximum procedure safety, prostate biopsy will be a TRUS-guided targeted transperineal biopsy and bone biopsy will be CT-guided using an automated drill. Moreover, to identify the imaging modality with the highest accuracy in detecting bone-metastatic prostate cancer at first presentation, an additional whole-body MRI will be applied to patients on the study. Study participation will not affect the routine care for this stage of disease, which will start immediately after the biopsy samples have been acquired.

In Arm 2 tumour tissue samples will be acquired from prostatectomy specimens that patients are undergoing as part of their routine standard of care.

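### Sections 8.11 and 8.9 do not mask the hypoxia reader to the same man's paired sample or MRI hypoxia map, so stain-based primary-bone co-existence and MRI validation could be inflated by the reading

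*Protocol*

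**What the plan says.** Protocol section 8.11 gives a consultant histopathologist two tasks in one sentence. The first is diagnosis and Gleason grading. The second is to "allow assessment of the presence of intratumoural hypoxia as detected by immunohistochemical staining for pimonidazole", or by an alternative stain such as GLUT1 if the man did not take pimonidazole. Section 8.11 continues: "Hypoxic areas will be marked to guide microdissection for subsequent nucleic acid extraction from the respective slides".

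The hypoxia call then enters two comparisons.

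- **Primary against bone (Arm 1).** Under section 7, the stain results and "the 28-gene RNA expression of the samples will be compared for each patient to identify co-existent hypoxia in primary PCa and paired bone metastases".
- **MRI against stain (Arm 2).** Under section 8.9, the MRI sequences "aim to detect hypoxic sub-regions of tumour that can be validated against pimonidazole staining regions following prostatectomy". Both scans come before the prostatectomy.

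Neither section mentions coded slides, a reading order, masking to the paired sample or the MRI, or a point at which readings or MRI regions are locked. Section 8.9 does not say who draws the MRI regions.

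**The concern.** Whether a section shows hypoxia, and where its edge lies, is judged by eye. If the reader knows that the man's other sample was positive, or where the MRI placed the hypoxic sub-region, a doubtful area may be called to match. Agreement would then arise from the reading and not from the tumour.

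The protocol makes such knowledge plausible. The schedule in section 5 puts the prostate and bone biopsies at the same visit. Section 8.3 prefers diagnostic and research prostate sampling in one procedure and uses the bone biopsy to confirm metastatic disease. Diagnostic work-up is normally done on identified patients, so a reader with that role could know whose slide it is and what the other specimen showed. In Arm 2, MRI hypoxia maps can exist before any stain is read.

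At stake are the co-existence aim in section 7 and hypothesis 7 in section 6.4, that MRI can detect hypoxic sub-regions. No later analysis can restore masking that was absent when the slides were read.

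**Working it through.** The protocol states no agreement figure, threshold, test or power, so there is nothing to reproduce. Section 9.2 says that no power calculation was done. What follows illustrates sensitivity; it does not estimate bias in this study.

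**Inputs**

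- Pairs: at most 30 primary-bone pairs in Arm 1 (section 9.2: 15 + 15). There may be fewer fresh pairs, because "Patients declining a second prostate biopsy will be eligible and will undergo the bone biopsy only" (section 8.1).
- Prevalence of hypoxia, p: 50%, from the statement in section 6.1 about solid tumours in general. A range of 30-70% is assumed, the same at both sites.
- Pull fraction, f: the share of second readings that copy the first. Assumed 10%, 20% and 30%; the documents give no value.

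**Model for paired yes/no readings, with the two sites truly unrelated**

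- Chance agreement: a = p² + (1 − p)²
- Observed agreement: A = f + (1 − f) × a
- Kappa = (A − a) / (1 − a) = f

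At p = 0.5, a = 0.25 + 0.25 = 0.50. With f = 0.2, A = 0.2 + 0.8 × 0.50 = 0.60 and kappa = 0.10 / 0.50 = 0.20.

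At p = 0.3 or 0.7, a = 0.09 + 0.49 = 0.58. With f = 0.2, A = 0.2 + 0.8 × 0.58 = 0.664 and kappa = 0.084 / 0.42 = 0.20.

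The last two columns give the chance that an exact one-sided 5% binomial test on 30 pairs would declare agreement above chance. The protocol plans no such test; it serves only as a yardstick.

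| f | Kappa | Agreement, p = 50% | Agreement, p = 30% or 70% | Declared, p = 50% (20 or more of 30 agree) | Declared, p = 30% or 70% (23 or more of 30 agree) |
|---|---|---|---|---|---|
| 0 | 0 | 50% | 58% | 4.9% | 2.7% |
| 10% | 0.10 | 55% | 62.2% | 13.5% | 7.1% |
| 20% | 0.20 | 60% | 66.4% | 29.1% | 15.9% |
| 30% | 0.30 | 65% | 70.6% | 50.8% | 30.6% |

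With 20 pairs and p = 50%, the chance goes from 2.1% at f = 0 to 5.5%, 12.6% and 24.5%.

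**If the sites are truly related.** With a true kappa of 0.40, observed kappa = f + (1 − f) × 0.40. For f = 10%, 20% and 30% this gives 0.46, 0.52 and 0.58.

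**For scale.** The 95% half-width of an agreement near 50% is 1.96 × √(0.25 / 30) = 0.179, about 18 percentage points with 30 pairs. With 20 pairs it is about 22 points. The illustrated shifts of 5 to 15 points lie within sampling error, so one study could not separate them from chance or from biology.

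**What the model leaves out.** The Arm 2 comparison sets MRI sub-regions against stained regions, which is a question of spatial overlap. A yes/no kappa does not describe it, and no figure is offered for it. MRI is also optional: "Any patients not agreeing to undergo additional MRI scans are still able to be enrolled into Arm 2 of the trial", so fewer than 30 MRI-tissue pairs are possible.

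**The case against.** The strongest objection is that the protocol is silent on masking; it does not prescribe an unmasked reading. A laboratory procedure could cover the matter, although neither 8.11 nor 8.9 cites one. This stands, and it limits the point to a possible bias. It does not remove the point: who reads a slide, and with what knowledge, is part of how the measurement is made, so the statistical analysis plan, which was not available, would not normally settle it.

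Three stronger readings are tempting, and the documents do not support them.

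- A reader might infer that the histopathologist does see the man's other sample or MRI. Section 8.11 says nothing about access; it only fails to prevent it.
- A reader might blame the combination of grading and hypoxia scoring in one person. No aim or hypothesis relates Gleason grade to hypoxia, so knowing the grade distorts neither comparison. The dual role matters only as a route by which the reader may learn the paired result.
- A reader might conclude that the bias carries into the genomic comparison, because the marks choose the tissue that is sequenced. Neither direction nor size can be shown. Wrongly marked tissue could just as well dilute a contrast between hypoxic and other areas.

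Two further objections partly stand. The 28-gene signature is not scored by eye and gives a second measure of hypoxia at both sites. It is only partly independent, because section 7 measures it on microdissected tissue that the marks help select. Also, the study is an exploratory pilot with no agreement target. That excuses imprecision, but not a bias that is easily avoided, and section 8.9 presents the MRI work as validation.

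**Conclusion.** The point holds as a gap in the reading procedure. One reader does the diagnostic work-up, the hypoxia call and the marking, and nothing in 8.11 or 8.9 keeps the paired result or MRI map from that reader, or fixes MRI regions before staining is known. Stain-based co-existence and MRI validation could therefore be overstated. The MRI part depends on the histopathologist knowing the map, or on MRI regions being drawn with the stain known; the protocol neither describes nor excludes either.

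The size is unknown. The kappa range of 0.10-0.30 follows directly from an assumed pull of 10-30%, with unrelated sites and equal prevalence. It is not evidence about this trial. The case for acting is that the remedy is cheap and has to be in place before the slides are read.

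**What to change.** **Section 8.11.** Have the same histopathologist score and mark the hypoxia slides under coded numbers, in random order and apart from diagnostic grading, with one man's primary and bone slides not adjacent. Lock the calls and marked areas before the reader sees the paired stain result, the 28-gene score or any MRI hypoxia map. Tissue type cannot be hidden, since bone and prostate look different, but the man's identity and his linked results can.

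**Section 8.9.** Require the MRI hypoxia regions to be fixed before the staining result is available to whoever draws them.

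**Cost.** Slide coding, a random reading list and a short delay before the research reading. No second reader, extra tissue or extra patients are needed.

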8.12 Assessment of circulating tumour cells (CTCs) and circulating tumour DNA (ctDNA)

In collaboration with the CRUK Manchester Institute Cancer Biomarker Centre (CBC) ([name]) blood samples will be used to assess the prevalence and origin of CTCs and ctDNA. Previous studies have demonstrated that the presence of 5 or more CTCs at baseline, as determined using the CellSearch platform, are a prognostic factor for overall survival in metastatic prostate cancer [14, 15]. Although the CellSearch assay is the only FDA-approved method for CTC detection in prostate cancer, the fact that the system relies on CTCs expressing EpCAM antigen for capture means that CellSearch compares unfavourably with marker-independent platforms for CTC capture in this disease [16]. The CRUK MI CBC have extensive experience of CTC analysis in a variety of clinical settings, and have developed a number of platforms and methods for CTC

capture and analysis. In addition to the CellSearch platform, in routine use in the CBC are microfluidics-based, marker independent CTC enrichment systems (Parsortix, ClearCellFX), and also slide-based “no cell is lost” capture systems (RareCyte, High-Definition Single Cell Analysis, HD-SCA). These marker-independent platforms are amenable to the study of CTCs in prostate cancer. For this study CTCs will be enriched using the Parsortix platform and enumerated and characterised using bespoke assays developed by CBC. Characterisation will include staining of captured cells for known CTC and exclusion markers, plus if required bespoke staining assays can be developed for markers relevant to prostate cancer, e.g. AR, PTEN. Additionally, single CTCs can be isolated for genomic analysis to complement analysis of the tumour genome, and analysis of ctDNA. CTC genomes will then be compared to primary and metastatic lesions to determine their origin(s). Moreover, it will be assessed if CTC genomes are enriched for hypoxic regions (based on pimonidazole labelling or an alternative hypoxia biomarker such as GLUT1).

Profiling of ctDNA is a key aspect of the work of the Nucleic Acid Biomarkers (NAB) team, and which complements the CTC analysis outlined above. The NAB team has developed methods for the isolation of ctDNA from patient samples, and also analytical approaches including gene copy number variation (CNV), targeted sequencing using droplet-digital PCR and selected gene panels, and discovery approaches such as whole exome sequencing (WES). There are a number of examples where analysis of ctDNA from patient blood samples has confirmed and extended detections of mutations in primary tumours and metastases in prostate cancer (e.g. [17, 18]). Analysis of patient ctDNA is particularly amenable to the stated aims of this study, specifically assessing the genomic aberrations in hormone-naïve primary prostate cancer, and determining genomic instability driving early spread. Certain genomic aberrations have been documented as prognostic in metastatic prostate cancer, including androgen receptor point mutations and splice variants [19-21], PTEN loss which is associated with decreased AR activity [22], and mutations in DNA repair genes [23]. A panel of these genes for targeted sequence analysis based on ctDNA will be applied, consistent with the biopsy-driven analysis described earlier.

8.13 Storage and use of tissue and blood sample left-overs

Patients participating in this study also consent that any unused samples at the end of this study will be gifted to the Manchester Cancer Research Centre (MCRC) Biobank for use in future research projects. The MCRC Biobank makes samples available to all kinds of researchers, including pharmaceutical companies for all kinds of cancer research and genetic studies. Access to Biobank samples is strictly regulated and the samples will only ever be released for high quality cancer research projects approved by

the MCRC Biobank Access Committee. Researchers using samples will only ever receive anonymised data and personal identifiable information will be kept strictly confidential.

9. PATIENT SELECTION AND RECRUITMENT

9.1 Patient Identification

Patients eligible for study inclusion will be identified from their medical records after routine staging procedures for newly diagnosed prostate cancer during the respective multidisciplinary team meeting (MDTs) or patient referral pathway and then be informed of this study by their local clinical care team within the respective urology clinics at the University Hospital of South Manchester NHS Foundation Trust in Wythenshawe (Urology consultant: [name]), The Royal Oldham Hospital (Urology consultant: [name]), and The Salford Royal NHS Foundation Trust (Urology consultants: [name], [name]).

The local clinical care team provides eligible patients with the participant information leaflet and requests the patient to allow the study staff at The Christie NHS Foundation Trust to contact the patient to evaluate his interest in study participation. If a patient is willing to participate in the HYPROGEN study an appointment at The Christie outpatient research clinic for another, detailed recapitulation of the studies' aims and potential risks and benefits of study participation will be scheduled for within the next 5 working days (consent visit). Patients that are either not suitable for inclusion or whom do not wish to participate will continue along the routine care pathway.

9.2 Sample Size

A total number of 60 patients will be recruited into this pilot study, 30 patients with metastatic disease in Arm 1 and 30 patients with localised prostate cancer in Arm 2. Within Arm 1, 15 patients with a high disease burden identified as a number of bone metastases ≥ 5 with or without visceral metastases (cohort A) and 15 with a low burden of bone metastases defined as ≤ 4 bone metastases and no signs of visceral disease (cohort B) detected on routine bone scan imaging. As this is a feasibility study, no power calculation was applied for patient number estimation.

9.3 Patient Selection Criteria

All patients must meet all of the inclusion criteria and none of the exclusion criteria for this study at the time of registration. Under no circumstances can there be exceptions to this rule.

9.4 Inclusion Criteria

Arm 1

No	Inclusion Criteria Patients are eligible only if they meet all of the following criteria
1	Male patients aged 18 years and older
2	Histologically proven adenocarcinoma of the prostate (\geq cT2) OR Highly suspected metastatic prostate cancer
3	PSA value of \geq 20 ng/mL
4	Multiple lesions (\geq 5) suspicious of metastatic spread on routine imaging procedures with at least one amenable* to biopsy (cohort A) OR oligometastatic bone disease (\geq 1 to \leq 4) at routine bone scan with at least one lesion amenable* to biopsy (cohort B) *e.g. safely to biopsy and expectably providing sufficient tissue yield
5	World Health Organisation (WHO) performance status 0 to 2 with no deterioration over the previous 2 weeks and minimum life expectancy of 12 months
6	No prior local and/or systemic treatment for localised prostate cancer
7	Willing to donate cancer tissue samples for research purposes (bone metastasis and primary tumour)

Arm 2

No	Inclusion Criteria Patients are eligible only if they meet all of the following criteria
1	Male patients aged 18 years and older cT ₂ -T ₃ / cN ₀ -N ₁ / cM ₀ Any Group Grade (GG) 2-5: this includes Gleason scores 3+4, 4+3, 4+4, 4+5, 5+3, 5+4, 5+5. Any PSA
2	Histologically proven adenocarcinoma of the prostate
3	Planned radical prostatectomy as primary treatment for localised prostate cancer
4	World Health Organisation (WHO) performance status 0 to 2 with no deterioration over the previous 2 weeks and minimum life expectancy of 12 months
5	No prior local and/or systemic treatment for localised prostate cancer
6	Willing to donate cancer tissue samples for research purposes (any metastasis and primary tumour)

